A Phase One Study Investigating the Tolerability and Effects of AZD0530 on Functional Neuroimaging Response in Individuals With or Without a Family History of Alcoholism

NCT02262026

12/17/18

“Functional Neuroimaging of Alcoholism Vulnerability: Glutamate, Reward, Impulsivity, and Pavlovian-to-Instrumental Transfer (PIT), Part II - Saracatinib”

1. Introduction:

The purpose of this pilot study is to evaluate the role of Saracatinib in clarifying the neurobiology of alcoholism risk. This is a 1-site, randomized, within subjects, counterbalanced double-blind study of one dose (125 mg) of Saracatinib and placebo. This project explores the effects of 1 dose of Saracatinib (an experimental Fyn-Src family protein tyrosine kinase inhibitor drug (AZD0530)), in a double-blind, randomized, counterbalanced manner on alcoholism risk-relevant tasks. Drug/placebo will be administered on 2 separate visits separated by 1 week following an initial screening visit. More specifically, this project examines 4 functional MRI tasks related to different aspects of reward and/or impulsivity-related behavior in different contexts, compares the underlying neural circuitry across tasks, and uses a pharmacologic probe of the glutamatergic system to examine N-methyl-D-Aspartate and Dopamine (NMDA/DA) interactions. The combined measures provide the opportunity to advance our understanding of specific aspects of brain function related to familial alcoholism vulnerability in an already well-characterized population as some members evolve into alcohol abuse. In addition, as well as conventional within-task analyses, functional network connectivity and allied approaches will be used to examine brain networks across the above tasks.

2. Background:

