Subjects will either have a family history of alcoholism (FHP) or no family history of alcoholism (FHN; N=45 per group, to a total of 90 subjects; males and females in equal numbers). We will recruit subjects from the general population by advertisement (e.g. in the Hartford Advocate or on Craig's List). Yale University will provide and pay for an encrypted, password-protected study cell phone to contact potential subjects via text message. Subjects will also have the opportunity to agree to text message appointment reminders in the informed consent form. Interested participants will also have the chance to respond to web based advertisements that include the option to call in to be screened for eligibility over the telephone or via a locked online survey database. If participants complete the online pre-screener and are found eligible they will then be contacted to be fully screened by the staff recruiter to determine complete eligibility.

The CTNA study coordinator screens all potential subjects obtained from the above sources, and a study FH status is determined using the family history approach operationalized by the Family History Assessment Module (FHAM), developed by COGA. FHPs are defined as having a parent and at least another first- or second-degree relative with alcohol dependence OR having at least a father with a history of alcoholism. If the affected parent is the mother, we will rule out possible fetal alcohol syndrome, using a standardized symptom checklist; FHN will have no affected first-degree relative. We will be selecting subjects from families with substantial risk for developing alcoholism, and this increased susceptibility probably reflects increased genetic liability.

5.3a Inclusion Criteria:

Inclusion criteria are equal numbers of men and women between the ages of 18 and 40 years. Recruitment will be through advertisement. On each test day, subjects will be first screened toxicologically for drugs of abuse (and for women of childbearing age, pregnancy) by urine testing, any positive test results in exclusion. Our participants will not come from a "vulnerable population" because participants will not be pregnant women, under legal coercion or restriction,

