ketoconazole, macrolides, miconazole, nefazodone, omeprazole, ritonavir, docetaxel, aromatase inhibitors & verapamil. Other exclusions are absolute neutrophil count <2,000/micro-L, platelets <150x10³/micro-L, AST, ALT, total bilirubin >1.5 x upper limit of normal (ULN); serum creatinine, >2 x ULN, significant EKG abnormality, or history of interstitial lung disease. Subjects will be administered a visual analog intoxication scale every 30 minutes by verbally stating symptomology on a rating scale, and heart rate and blood pressure will be checked hourly. At the end of each study day, subjects will only be allowed to be discharged when they have minimal subjective reports of intoxication or sedation, vital signs have returned to baseline, and they have been assessed by either an RN or MD. Participants will be questioned carefully regarding possible study drug-related side effects at each visit using a standardized screening checklist (the SAFTEE-see below) and be followed up 1 week after the final test day by telephone screen. The SAFTEE is a tool for systematic assessment of adverse effects in clinical trials which includes 1) open-ended questions about any changes in physical or health problems, appearance, or activity level, and 2) yes/no responses to a specific list of symptoms (which correspond to anticipated adverse events associated with Saracatinib). For each symptom reported, the date of onset, severity (minimal, mild, moderate, severe), whether it was drug-related, and action taken, is recorded. The SAFTEE will be administered at each dosing day and at post-study follow up, to monitor and document rates of adverse events in a standardized manner.

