Side effects/adverse experiences are collected on standardized forms, using the SAFTEE (Levine and Schooler, 1986). The SAFTEE includes 1) open-ended questions about any changes in physical or health problems, appearance, or activity level, and 2) yes/no questions on a specific list of symptoms (which correspond to anticipated adverse events associated with Saracatinib) for a specified time period. For each symptom reported on the SAFTEE a rater also records the date of onset, severity (minimal, mild, moderate, severe), whether it was drug-related, and action taken. The SAFTEE is administered at baseline, during the inpatient periods, and every other day during the outpatient treatment periods. We will monitor the number of patients experiencing symptoms and the severity of symptoms.

Adverse events will be monitored for each subject participating in the study and attributed to the study procedures / design by the principal investigator, [name], according to the following categories:

- a.) Definite: Adverse event is clearly related to investigational procedures(s)/agent(s).
- b.) Probable: Adverse event is likely related to investigational procedures(s)/agent(s).
- c.) Possible: Adverse event may be related to investigational procedures(s)/agent(s).
- d.) Unlikely: Adverse event is likely not to be related to the investigational procedures(s)/agent(s).
- e.) Unrelated: Adverse event is clearly not related to investigational procedures(s)/agent(s).

The following scale will be used in grading the severity of adverse events noted during the study:

- 1. Mild adverse event
- 2. Moderate adverse event
- 3. Severe

An adverse event may be graded as severe but still not meet the criteria for a Serious Adverse Event. Similarly, an adverse event may be graded as moderate but still meet the criteria for an SAE. It is important for the PI to consider the grade of the event as well as its “seriousness” when determining whether reporting to the IRB is necessary.

The principal investigator, [name], will conduct a review of all adverse events upon completion of every study subject. The principal investigator will evaluate the frequency and severity of the adverse events, report to both the HH and Yale IRB’s plus the DSMB and determine collectively if modifications to the protocol or consent form are required.

DSMB.

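### Tolerability is in the title and each participant is their own placebo control, yet no saracatinib-versus-placebo comparison of adverse events or other safety measures is planned

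*Combined protocol and SAP*

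**What the plan says.** The title is "A Phase One Study Investigating the Tolerability and Effects of AZD0530 on Functional Neuroimaging Response". The Introduction describes a "randomized, within subjects, counterbalanced double-blind study of one dose (125 mg) of Saracatinib and placebo" and adds: "Drug/placebo will be administered on 2 separate visits separated by 1 week". Section 5.2 sets "N=45 per group, to a total of 90 subjects".

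Adverse events are handled in two places.

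- The closing text of Section 5.3b states: "The SAFTEE will be administered at each dosing day and at post-study follow up". For each reported symptom, "the date of onset, severity (minimal, mild, moderate, severe), whether it was drug-related, and action taken, is recorded".
- Section 7 (Plan for Grading Adverse Events and Attribution of Adverse Events) repeats those items but gives a different SAFTEE schedule: baseline, inpatient periods, and alternate days as an outpatient. It then states the use: "We will monitor the number of patients experiencing symptoms and the severity of symptoms". The principal investigator attributes events on a five-level scale, grades them on a three-level scale, and reviews frequency and severity after each participant finishes.

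Other safety data are collected: laboratory tests (Section 2a, Choice of drug Doses), EKG (end of Section 4), and hourly vital signs with a half-hourly intoxication scale (Section 5.3b). Their stated roles are detecting events and deciding on discharge.

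Section 6 covers fMRI processing and the analyses for Aims 1 to 4. Treatment enters as a within-subject factor for BOLD, BART and EDT outcomes. No safety or tolerability outcome appears.

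**The concern.** A reader of this title will expect the report to say how saracatinib was tolerated relative to placebo. The design supplies what is needed: each person is seen under both treatments in randomized order. The plan uses that pairing for imaging and tasks but not for tolerability.

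Without a comparison, the tolerability statement rests on two weak supports. One is a count of people with symptoms and no stated comparator. The other is relatedness, judged event by event. The side effects listed in Section 7 include headache, nausea, diarrhea and flu-like symptoms, which people also report without a drug, and a study day lasts about seven hours. Relatedness judgement also depends on blinding, which is double-blind in the Introduction and single-blind in Section 3.

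The conclusion could err either way: background complaints could be read as drug effects, or a real excess dismissed as background.

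**Working it through.** The documents state no adverse-event rate, alpha, power or margin for tolerability, so there is no figure to reproduce. Only 45 + 45 = 90 can be checked, and it agrees. All rates below are assumptions.

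**1. What a count without a comparator shows.** Let p be the chance of reporting a symptom at a visit, the same on drug and placebo, with visits independent. The share reporting it at least once over two visits is 1 − (1 − p)².

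- p = 0.10: 1 − 0.90² = 19%
- p = 0.20: 1 − 0.80² = 36%
- p = 0.30: 1 − 0.70² = 51%

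The true drug effect is zero in each line.

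**2. What a paired comparison would give.** Let a be the share with the symptom on saracatinib only and b the share on placebo only. The risk difference is a − b, and its 95% half-width is 1.96 × √{[a + b − (a − b)²] / n}. For a = 0.20, b = 0.05, n = 90: 1.96 × √(0.2275 / 90) = 0.099. Power is for the exact McNemar test, two-sided 0.05.

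| a / b | Difference (points) | Half-width, 90 pairs | Power, 90 pairs | Half-width, 72 pairs | Power, 72 pairs |
|---|---|---|---|---|---|
| 10% / 5% | 5 | 7.9 | 16% | 8.9 | 12% |
| 15% / 10% | 5 | 10.3 | 11% | 11.5 | 9% |
| 15% / 5% | 10 | 9.0 | 49% | 10.1 | 39% |
| 20% / 10% | 10 | 11.1 | 33% | 12.4 | 27% |
| 20% / 5% | 15 | 9.9 | 79% | 11.0 | 68% |
| 25% / 10% | 15 | 11.8 | 62% | 13.2 | 51% |

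The 72-pair columns assume 20% loss (90 × 0.8); Section 5.4 mentions frequent cancellations. Power is 11% to 49% for differences of 5 to 10 points with 90 pairs, so an interval is informative where a test mostly is not.

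**3. Why onset date should decide the treatment.** Suppose events were tabulated by the contact at which they were reported, and a share f began after the participant left. Write D and P for the true event rates on drug and placebo. If events from the final phone call are booked to visit 2:

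- drug-first order: (1 − f)D − [fD + P] = (1 − 2f)D − P
- placebo-first order: [D + fP] − (1 − f)P = D − (1 − 2f)P
- average of the two orders: (1 − f)(D − P)

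If events from that call are booked to neither visit, the same steps give (1 − 1.5f)(D − P). For an assumed true difference of 15 points and f = 0.5, these give 7.5 and 3.75 points. The documents supply no f, D or P, and state no tabulation by contact, so this shows direction only.

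**The case against.** The strongest reply is that tolerability appears only in the title. The stated purposes concern neurobiology and effect sizes, none of the six numbered aims or hypotheses is about tolerability, and Section 7 is a monitoring plan, not an analysis plan. Participants are protected by investigator review after each person, a DSMB that includes a statistician and sees safety reports twice a year, a 24-hour line, and laboratory and EKG checks before each further visit. This stands as far as it goes: what is missing is an analysis and its tables, not safety oversight. A reader might infer that participants are unprotected; the documents do not support that.

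Other tempting readings also go too far.

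- *The plan only counts symptoms.* Severity, laboratory values, EKG, vital signs and intoxication ratings are collected, and relatedness is recorded by a SAFTEE rater as well as by the investigator. The gap is that none has a treatment comparison.
- *The planned tabulation is biased toward no difference, so a real excess will be missed.* No text says events will be tabulated by contact, and onset dates are recorded. The alternate-day schedule in Section 7, if it applied between visits, would catch most delayed events before visit 2. It conflicts with Section 5.3b and fits two single-dose visits poorly, but it cannot be ignored.

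Two statements could be offered as covering the point: Section 5.1 speaks of effect size against placebo, and Section 7 says the hospital's reporting system follows and analyses events. Neither specifies a comparison of adverse events by treatment.

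**Conclusion.** The omission is real. Section 6 plans no saracatinib-versus-placebo comparison of any tolerability measure, although the paired data will exist and the title raises the question. Counts, severity grades and relatedness judgements cannot by themselves separate drug effects from background symptoms.

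Its effect on the conclusion cannot be sized, because the documents give no rates. Under the assumed rates, background alone could put 19% to 51% of participants in the symptom count, while a paired estimate from 90 complete pairs would carry a half-width of about 8 to 12 points. Misassignment of delayed events is a hazard to guard against, not a flaw shown in the plan.

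This rests on the two-visit, single-dose design in the Introduction. Section 3 also mentions three experimental visits and Section 7 a second dose level; those passages must be reconciled.

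**What to change.** Add a short tolerability analysis to Section 6.

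- **Assignment.** Assign each SAFTEE event by its recorded onset date to the most recent dose received. Events starting before the first dose belong to neither treatment.
- **Symptoms.** For any symptom and for each listed symptom, report number and percentage by treatment, and the paired saracatinib-minus-placebo risk difference with 95% confidence interval. Allow for visit order, for example by estimating the difference within each order and averaging the two. Estimates lead; any McNemar test is supportive only.
- **Other measures.** Report vital signs, intoxication scale, laboratory values and EKG as within-person treatment differences from a model with treatment and period terms. State the period term explicitly, since the Section 6b models list none.
- **Relatedness.** Keep it as a secondary summary, and reconcile the double-blind and single-blind statements.
- **Consistency.** Reconcile the SAFTEE schedules in Sections 5.3b and 7, and state how the four SAFTEE severity levels map to the three-level grade.

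The cost is a page of text, a few tables and wide intervals. Onset dates and all the measures are already collected.
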